1. SYNOPSIS

The elderly patient demented in an acute geriatric department: pilot study, monocentric, randomized on the use of aromatherapy as a complementary treatment tool to psychopharmacology in psychological disorders and behavior (BPSD).

Rationale

Behavioral and psycological symptoms of dementia (BPSD) are a big issue for families, paramedics, physician and the patient itself (1,2,3,4).

In absence of universally recognized guidelines, the standard of treatment of these disorders involves the use of psychotropic drugs (typical/atypical neuroleptics, antidepressants, benzodiazepines) that are often found to have a reduce efficacy and induce a number of side effects such as sedation, impaired motor neurons slowdown, cardiac electrical alterations and extrapyramidal syndrome (5,6,7,8,9). In consideration of this, it is important to check for treating alternative ways, which can reduce psychological and behavioural disorders and at the same time can reduce the use of psychotropic drugs.

Concerning the aromatherapy [10], the therapeutic use of natural essential oils, there are decades of clinical experience, especially in France, accompanied by increasing scientific evidence with significant increase in publications regarding its use of psychological disorders and dementia-related behavior context (11,12,13,14).

Based on the available scientific publications, it has been therefore decided to use two essential oils (*Citrus sinensis, Lavandula angustifolia*) in environmental diffusion within the Geriatric Department of the Clinic Luganese Moncucco.

Objectives

Primary objectives: through the execution of the Neuropsychiatric Inventory – Nursing Home Version (NPI-NH), the neuropsychiatric and psychopathological symptoms of dementia patients will be evaluated in order to assess how the use of aromatherapy can improve the management of BPSD, reducing, where there is clinical indication, psychotropic therapy and secondary side effects. The score is considered positive if the presence of BPSD is greater than or equal to 1 (15, 16,17); the improvement of the score is represented from decrease of the NPI-NH respect to the initial assessment (19, 20).Performing neuropsychological tests is not an additional attention to enrolled patients, but it is part of clinical practice (18).

Secondary objectives: to validate the hypothesis that through the use of aromatherapy will improved the management of Behavioral and psycological symptoms of dementia (BPSD) in the dementia patient, with a concomitant reduction of the clinical staff stress who take care of patients (physician, nurses, care assistants), determined by the results reported by the Neuropsychiatric Inventory – Nursing Home Version (NPI-NH), In the specific section concerning

the distress measurement; improvement of the score is represented from decrease of the NPI-NH respect to the initial assessment (19, 20).

Project duration: 2 months of enrollment.

Number of patients: 32, 16 patients for the control group and 16 patients for the group" aromatherapy".

Inclusion criteria:

- patients age \geq 70 years;

- patients admitted to the acute geriatrics ward;

- patients with known diagnosis of dementia associated with BPSD or diagnosis performed during hospitalization.

Exclusion criteria:

- patients with alcohol-based dementia;
- patients with Mild Cognitive Impairment (MCI) paragraph 4;
- patients with language barriers;
- patients already being treated with aromatherapy.

Protocol design: prospective data collection of psychological disorders and behaviour in patients with diagnosis of dementia with associated behavioral and psycological symptoms of dementia (BPSD)- diagnosis already performed using neuropsychological tests (below), according Evidence Based Medicine, and/or patients who BPSD diagnosis performed during the hospital stay in the Geriatric Competence Centre, Clinica Luganese Moncucco.

The enrollment will be performed in May and June 2018.

Enrolled patients will be treated with psychotropic drugs vs psychotropic drugs with aromatherapy in environmental diffusion. It is expected to use neuropsychological specific tests to assess dementia, motor and functional status patient status (CAM - Confusion Assessment Method -, CDR - Clinical Dementia Rating -, MMSE - Mini Mental State Examination -, FAB - Frontal Assessment Battery -, Tinetti Scale, BADL - Basic Activities of Daily Living -, IADL - Instrumental Activities of Daily Living -, NPI-NH – Neuropsychiatric Inventory – Nursing Home Version)).

Patients enrolled in the project will not undergo to additional tests; the performed test are required in the standard clinical practice [18].

GROUP A: 16 patients, following the inclusion criteria, will be enroll and they will be treated with psychotropic drugs.

GROUP B: 16 patients, following the inclusion criteria, will be enroll and they will be treated with psychotropic drugs and, in a complementary way, with aromatherapy in environmental diffusion.

3. STUDY CHARACTERISTIC

Monocentric, randomized, pilot study which consists in the prospective data collection related to psychological disorders and behavior in the patient with dementia using neuropsychological tests in order to define the possible effectiveness of two essential oils (*Citrus sinensis, Lavandula angustifolia*) in the disorders control of psychological sphere and behavior of patients with degenerative or mixed type of dementia, admitted in the Geriatric Department of Clinica Luganese Moncucco in May and June 2018.

In the proposal for therapeutic process of dementia patients in this project there is no disaccording with Evidence Based Medicine.

Patients enrolled in the project will not undergo additional tests; the performed tests will follow the standard procedures of clinical practice [18].

4. PROTOCOL RATIONALE

Behavioral and psycological symptoms of dementia (BPSD) are a major problem for families, physicians and the patient itself [1,2,3,4].

Performing neuropsychological tests is not an additional source of distress for enlisted patients, but is part of clinical practice [18].

The standard treatment of these disorders involves the use of psychotropic drugs (typical/atypical neuroleptics, antidepressants, benzodiazepines) which are often ineffective and have a number of side effects such as sedation, reduction in cognitive performance, cardiac electrical alterations and extrapyramidal syndrome [5,6,7,8,9].

Within the scientific community, it is therefore mandatory to identify alternative ways of managing BPSDs, which can have a beneficial effect on patient life and, at the same time, a reduction in the used of psychotropic drugs.

The therapeutic use of natural essential oils has decades of clinical experience, especially in France, accompanied by an increase numbers of publications in their use in BPSD [11,12,13,14].

The knowledge of alternative treatments of BPSD (such as aromatherapy) are the basis of our study project, which involves the introduction of essential oils in the BPSD management, while maintaining conventional psychotropic therapy (typical/atypical neuroleptics, antidepressants, benzodiazepines) in a prefixed form of ProReNata (PRN) (paragraph 5).

The identified oils (*Citrus sinensis, Lavender angustifolia*) were selected on the degree of purity defined by the mass spectrophotometry available by the supplier.999

The choice of adjuvant therapy with essential oils could allow, in accordance with the 3rd principle of Medical Ethics to administer natural treatment to patients with distress with BPSD reducing, if possible, use of psychotropic drugs and their major side effects.

The use of essential oils in treatment of BPSD can also have a positive impact on patient economic management due to limited costs, allowing a distribution of treatments according to IV Principle of Ethics Medical: principle of justice.

Mild Cognitive Impairment (MCI) patients were excluded from the protocol as a form of predementia.[21].

MCI is a neurological syndrome characterized by a cognitive impairment greater than that statistically expected based on age and education level, but who are still able to carry out their daily activities (BADL and IADL tests). The Mild Cognitive Impairment is considered a form of predementia, situated in a transition point between normal aging and dementia.

5. STUDY POPULATION

The population that will be evaluated within the project is constitute by patients with diagnosed dementia with BPSD (diagnosis carried out using, according to Evidence Based Medicine, the neuropsychological tests below) and/or by patients who the diagnosis of dementia with BPSD will be performed at the Geriatric Competence Centre of the Clinica Luganese Moncucco.

The enrollment will be performed in May and June 2018.

All patients mentioned above, within 48 hours after the admission at the Geriatric Department or the manifestation of BPSD, will be assessed to neuropsychological and functional tests (CAM - Confusion Assessment Method -, CDR - Clinical Dementia Rating Score -, MMSE - Mini Mental State Examination -, FAB - Frontal Assessment Battery -, scala di Tinetti, BADL - Basic Activities of Daily Living -, IADL - Instrumental Activities of Daily Living -), as required by Good Clinical Practice[18]. Subsequently, patients who can be enrolled in the study will be randomized into two groups, described below.

Here is the study population on which we will focus:

GROUP A – **controls** -: will be enrolled 16 patients eligible for criteria of inclusion, treated with psychotropic drugs.

GROUP B – aromatherapy –: will be enrolled 16 patients eligible for criteria of inclusion, treated with psychotropic drugs and aromatherapy in air-diffusion.

Based on the randomization, patients will be divided into group A - controls - and group B - aromatherapy in air diffusion.

Neuropsychiatric Inventory (NPI) is a validated and useful tool for characterizing and assessing the BPSD frequency and seriousness.

A Resident Physician will perform the NPI in our study protocol.

The physician, by interview with patient's nurse, in absence of patient himself, will fill out the NPI-NH.

The above mentioned physician, formerly operating in the Geriatric Department – who knows the geriatric assessments - and currently active in the Rheumatology Department, will therefore respect the blind study procedure.

The geriatric nurse was chosen for the close relationship of care that is created with the patient; during the test, BPSD frequency and seriousness will be evaluated.

The psychological distress induced by BPSD patients, will be evaluated on the three figures who have in charge the patient, which are nurses, care assistants and the resident physicians.

The psychological distress assessment is part of the NPI-NH test with a scale of severity from 0 to 5.

Nurses will be undergo to NPI – NH test within 48 hours after patient admission or at first appearance of BPSD **(T1), T2 (T1-3 days)** 3 days after enrollment, at **T3 (T1-6 days)** 6 days after enrollment, at **T4 (T1-12 days)** at 14th day. According to the same timing, NPI-NH will also be performed to the resident physicians, the nurses and the care assistants to assess the psychological distress. The NPI-NH test will be performed following the Good Clinical Practice.

The tests results performed to the two groups of patients will be considered in order to assess a possible reduction in BPSD. As the project is a pilot study, a descriptive analysis will be performed.

Here the schemes defined for treatment with aromatherapy and psychotropic drugs, according to scientific publications in the first case and scientific publications and Evidence Based Medicine in the second:

Aromatherapy

Route of administration: air diffusion with ultrasonic diffuser in a single room and for about an hour.

Doses:

- Citrus sinensis: 6 drops at 8, 12 and 18 in nebulization

and

- Lavender angustifolia: 6 drops 8 p.m. in nebulization

PRN PSYCOPHARMACOTHERAPY

Drug:

- in case of psychomotor agitation:

Haloperidol 1 mg PO 10 times in 24 hours

1 mg SC/IM 5 times in 24 hours

Reperidone 0.5mg - 2mg PO in 24 hours *Olanzapine* 2.5 mg – 5 mg PO in 24 hours

Clozapine 6.25 mg – 25 mg PO in 24 hours

Quetiapine 12.5mg - 150mg PO in 24 hours

- in case of sleep disturbance:

Valerian 1 tb - 2 tbs PO in 24 hours Melatonin 1 tb - 2 tbs PO in 24 hours Lorazepam 0.5 mg - 3mg PO in 24 hours Oxazepam 7.5mg - 45mg PO in 24 hours Clomethiazole 1 tb -3 tbs PO in 24 hours - in case of anxiety/depression: Trazodone 25 mg – 150 mg PO in 24 hours Escitalopram 10 mg – 20 mg PO in 24 hours Mirtazapine 15 mg – 45 mg PO in 24 hours

Citalopram 10 mg - 20 mg PO in 24 hours

Paroxetine 20 mg – 50 mg PO in 24 hours

The control group is treated with psychopharmacological therapy, defined by the PI, according to the Evidence Based Medicine criteria.

Patient can withdraw the ICF at any time.

The investigators could decide to withdraw a patient for safety and health.

The withdrawn patients will not be evaluated unless they have been treated for 8 days, useful to evaluate the aromatherapy efficacy.

In bibliography reported that essential oils in air diffusion are effective in 3 days. Additional 5 days of treatment allow to stabilize patient's condition and collect, through the NPI-NH test, changing in BPSD data.

Withdrawn patients will be followed according to the standards of care provided by the Clinica Luganese Moncucco.

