7. RANDOMIZATION

Enrolled patients with BPSD will be randomized according to the following randomization scheme (AABB, ABAB, BBAA, BABA, ABBA, BAAB).

A repetition of the first 4blocks will be performed, for a total of 32 patients, 16 each group, according to the following scheme:

AABB, ABAB, BBAA, BABA AABB, ABAB, BBAA, BABA

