8. PROJECT DESIGN

The project will be managed in the acute geriatric department of the Clinica Luganese Moncucco. Enrolment and treatment scheme is present in the flow chart (chapter 2).

After randomization patients will be enrolled in the two groups GROUP A, control group, and GROUP B, treatment group.

The enrollment will be performed in 2 months.

GROUP A: 16 patients, following the inclusion criteria, will be enroll and they will be treated with psychotropic drugs.

GROUP B: 16 patients, following the inclusion criteria, will be enroll and they will be treated with psychotropic drugs and, in a complementary way, with aromatherapy in environmental diffusion.

The project hypothesis will be validated using the following neuropsychological and functional tests:

- CAM (Confusion Assessment Method);
- CDR (Clinical Dementia Rating Score)
- MMSE (Mini Mental State Examination);
- FAB (Frontal Assessment Battery);

- Tinetti's scale;
- BADL (Basic Activities of Daily Living);
- IADL (Instrumental Activities of Daily Living);
- NPI-NH (Neuropsychiatric Inventory Nursing Home Version);

Neuropsychological tests are part of clinical practice [18].

Scientific reports show that essential oils in air diffusion are effective in 3 days. A final timepoints of 14 days represent the mean hospital stay:

2 days for the collection of behavioral data;

6 days to observe the possible effectiveness of aromatherapy in air diffusion;

6 days to adapt the therapy with oils and psychotropic drugs and stabilize patient's condition for a possible discharge.

Enrolled patients and nurses will be tested according to the following times:

8.1.1 Observation for 48 hours with data collection and execution of the NPI-NH (T1): in the 48 hours after patient admission at the Geriatric Department or at the diagnosis of dementia, the information collection will be performed: sensitive data (age, gender), dementia condition (CAM, CDR, MMSE, FAB), functional status (IADL, BADL, Tinetti scale) and the used number of psychotropic drugs. As a result of this evaluation, patient will be assessed for the presence of BPSD using the NPI-NH assessment scale, nurses will be undergo to NPI – NH test within 48 hours after patient admission. In case of a score greater than or equal to 1, patient will be followed within the study project, otherwise it will follow the standard process.

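### Protocol Sections 5, 7 and 8 give conflicting orders for randomisation and the baseline (T1) NPI-NH with its score-of-1 rule

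*Protocol*

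**What the plan says.** **Places that put T1 after randomisation.** Protocol Section 5 says that patients, within 48 hours of admission or of BPSD appearing, "will be assessed to neuropsychological and functional tests (CAM - Confusion Assessment Method -, CDR - Clinical Dementia Rating Score -, MMSE", and the list goes on to FAB, Tinetti, BADL and IADL. The NPI-NH is not in it. The next sentence is "Subsequently, patients who can be enrolled in the study will be randomized into two groups, described below". Section 8 says "After randomization patients will be enrolled in the two groups GROUP A, control group, and GROUP B, treatment group", and later "Enrolled patients and nurses will be tested according to the following times". The first of those times is T1 (8.1.1), where the entry rule appears: "In case of a score greater than or equal to 1, patient will be followed within the study project". Everyone else goes to the standard process. Section 9 does not list an NPI-NH threshold among the inclusion criteria.

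**Places that put T1 before or at randomisation.** Section 7 says "Enrolled patients with BPSD will be randomized", and Section 6 counts BPSD as present when the score is 1 or more. Section 8.1.1 treats the cognitive and functional battery and the NPI-NH as one T1 step in the first 48 hours. That is the same battery and window that Section 5 places ahead of randomisation. Section 8 also sets aside 2 days for behavioural data before the 6 days for observing an effect.

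**Blinding and analysis.** In Section 5 a physician from another department, described as blind, completes the NPI-NH by interviewing the patient's nurse. No blinding statement covers the nurse. Staff distress is collected at the same time points. The SAP compares T3 - T1 between arms with a Mann-Whitney test.

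**The concern.** T1 does two jobs: it decides who stays in the study, and it is the baseline of the change score that the SAP tests. Both should be settled before anyone involved in the rating can know the allocation. The protocol does not say this outright, and staff could follow it in either order.

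If they follow Sections 5 and 8 in sequence, two things become possible.

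- **Removal after allocation.** A patient allocated to an arm could then score 0 and return to standard care. The groups compared would no longer be the groups randomised, and the planned 16:16 split could be lost.
- **A baseline given with knowledge of the arm.** The treatment is a scent diffuser in the patient's room, and no sham is described for controls. A nurse who knows the allocation when describing symptoms at T1 could shift the baseline in one arm. Staff distress, the secondary outcome, is exposed in the same way.

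**Working it through.** **1. The plan's own figure.** The list printed in Section 7 has 8 blocks of 4, so 8 x 4 = 32, with 16 A and 16 B. This agrees with the stated 32 patients and 16 per group. It leaves no spare places for patients removed after allocation.

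**2. The order of events, side by side.**

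| Place in protocol | Order implied |
|---|---|
| Section 5 | battery without NPI-NH, then randomisation |
| Section 8, opening | randomisation, then enrolment in the groups |
| Section 8, schedule and 8.1.1 | enrolled patients tested at T1, then the score rule |
| Section 7 read with Section 6 | enrolment and score of at least 1, then randomisation |
| Section 8.1.1 read with Section 5 | battery and NPI-NH as one step in the window that precedes randomisation |
| Section 8, 2 + 6 + 6 days | data collection, then the effect period |

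The first three rows and the last three cannot all be followed literally. No sentence states the order of the NPI-NH and randomisation directly.

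**3. Effect of a shifted baseline.** Suppose T1 is raised by b points in Group B only. The change there becomes T3 - (T1 + b) = (T3 - T1) - b, so the between-arm difference in change moves by exactly b points. The protocol counts a fall in score as improvement, so an upward shift would look like benefit and a downward shift like harm. This holds for a descriptive summary as much as for a test.

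**4. Illustration of the false-positive rate.** Assumptions, none taken from the documents: no true effect, a two-sided 5% level, a t-test standing in for the Mann-Whitney test, and a shift d measured in SDs of the change score. With n = 16 per arm there are 30 degrees of freedom, the critical value is 2.042, and the noncentrality is d x sqrt(n/2) = d x 2.828.

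- d = 0.2: noncentrality 0.566, rejection 8.5%.
- d = 0.3: noncentrality 0.849, rejection 13.0%.

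The unit matters. If the shift is measured in SDs of T1, with equal SDs at T1 and T3 and correlation r, then d is divided by sqrt(2(1 - r)). The range for 0.2 to 0.3 becomes about 7.5% to 11% at r = 0.3 and 11% to 19% at r = 0.7.

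**5. Removals after allocation.** Let q be the share of randomised patients scoring 0 at T1. The documents do not give it, so it is assumed here. Expected removals are 32q, and the chance of at least one is 1 - (1 - q)^32. The last column is the chance that the two arms of 16 lose different numbers.

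| q | Expected removals | At least one | Unequal losses |
|---|---|---|---|
| 2% | 0.6 | 48% | 42% |
| 5% | 1.6 | 81% | 65% |
| 10% | 3.2 | 97% | 76% |
| 20% | 6.4 | >99% | 82% |

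**The case against.** The best reply is that the protocol intends T1 as screening. Section 7 with Section 6 makes a score of at least 1 a condition of randomisation. Section 5 randomises only patients who can be enrolled, and a score-0 patient would not be one of them. The NPI-NH is described separately later in Section 5, so its absence from the list does not by itself place it after allocation. The sentence "After randomization patients will be enrolled in the two groups" may mean only assignment to an arm. T1 also falls before the 6-day effect period: T4 is T1 plus 12 days and is called the 14th day, which puts T1 at about day 2. Section 8 refers to a flow chart for the enrolment scheme; it was not in the text available and may settle the matter.

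Much of this stands. A reader might infer that the protocol definitely places the baseline and its entry rule after randomisation, or that the nurse rates T1 knowing the arm. The documents support neither. The first takes one side of a contradiction as settled. On the second, the nurse is the informant and a physician described as blind completes the form. No sentence says that she knows the arm at T1. Whether she could depends on the unresolved order and on when the allocation is disclosed. The direction of any shift is also unknown.

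The reply does not remove the contradiction. Sections 5 and 8 can be followed literally to the wrong result, and no explicit sentence prevents it. Nor does the plan for descriptive analysis in Section 13 help, since a biased baseline distorts descriptive changes and the SAP does test significance.

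**Conclusion.** The concern holds as a conflict over order: Sections 5, 7 and 8 do not agree on whether the T1 NPI-NH and its score rule come before or after randomisation. It should be corrected, because T1 is both the gate to follow-up and the baseline of the tested change.

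The one-for-one effect of a baseline shift on the difference in change is exact. Whether any shift would occur, and its size and direction, are not known from the documents. The 8.5% to 13% is an illustration resting on an assumed shift of 0.2 to 0.3 SD of change and a t-test approximation. The number of score-0 removals is also unknown. It may be small, because entry already requires dementia with BPSD and the threshold is only 1. The baseline problem does not depend on that number.

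**What to change.** - **Section 5:** add the NPI-NH to the tests completed before randomisation.
- **Section 8.1.1:** state that the T1 NPI-NH and staff distress are completed, signed and dated, with a score of at least 1, before the patient's allocation is revealed and before diffusion starts.
- **Section 8, opening:** reword the sentence on enrolment after randomisation as assignment to groups, so that Sections 5, 7 and 8 give one order, and check the flow chart against it.
- **Score rule:** state that no patient is removed after allocation on the basis of the T1 score.

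The cost is wording only, within the existing 48-hour window. Patients scoring 0 become screening failures, so all 32 randomised stay in. At the assumed q of 2%, 5%, 10% and 20%, the number to screen is 32/(1 - q), rounded up: 33, 34, 36 and 40.

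Two related matters are separate and are not resolved by this change. The full allocation list is printed in Section 7, so reordering alone does not secure concealment. The 8-day rule for withdrawn patients in Section 5 also affects who is analysed.

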8.1.2 Assessment of NPI-NH at T2 (T1-3 days): 3 days after enrollment, patient will be re-evaluated with NPI-NH to assess BPSD progress. In addition, the distress level of on the three health caregivers is also measured with the NPI-NH test.

8.1.3 Assessment of NPI-NH at T3, assessment of vital parameters and use of drug reserves (T1-6 days): 6 days after enrollment, NPI-NH will be re-executed, with associated assessment of patient's vital signs (PAS, PAM, FC) and the use of psychotropic drug reserves.

8.1.4 Final T4 assessment (T1-12 days): NPI-NH scale will be performed in association with vital signs.

The physician in charge of dispensing the NPI-NH questionnaires to nurses to collect BPSD patients status, will also submit the questionnaires to the referring physician, nurse and care assistants with the aim to assess the level of stress in the clinical staff (see "Distress" column in NPI-NH questionnaire in the appendix).

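### Section 5 does not separate stopping study treatment from leaving the study, so a patient withdrawn before day 6 has no planned T3 score for the SAP's T3 − T1 comparison

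*Protocol*

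**What the plan says.** The withdrawal text at the end of Protocol section 5 gives two routes out of the study:

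- consent: "Patient can withdraw the ICF at any time";
- investigator decision: "The investigators could decide to withdraw a patient for safety and health".

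The second route withdraws the patient, not only the oils. No status exists for a patient who stops the oils, or any other study treatment, and stays under observation.

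Two rules then apply to everyone withdrawn by either route. The first is "The withdrawn patients will not be evaluated unless they have been treated for 8 days, useful to evaluate the aromatherapy efficacy". Its rationale is a 3-day onset of effect plus a further period: "Additional 5 days of treatment allow to stabilize patient's condition and collect, through the NPI-NH test, changing in BPSD data". The second is "Withdrawn patients will be followed according to the standards of care provided by the Clinica Luganese Moncucco".

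Sections 8.1.2 to 8.1.4 place the NPI-NH at T2 (day 3), T3 (day 6) and T4 (T1 + 12 days) for enrolled patients. Staff distress is rated on the same timetable (section 5). Neither section says what happens to these ratings after withdrawal. The SAP compares the groups on the change T3 − T1 and, in the text available, has no rule for withdrawn patients or missing scores.

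**The concern.** Section 6 aims to learn whether adding aromatherapy to psychotropic drugs reduces BPSD. A randomised comparison answers that only if outcomes are sought for everyone allocated. Here one status covers a patient whose treatment has been stopped but who could still be rated and a patient who refuses further data collection. Only the second has to be lost to follow-up.

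The loss falls on the score that the SAP analyses. It is triggered by events after randomisation, and those events may differ by arm. Only Group B has oils to stop, and section 12 names hypersensitivity to them as a risk. Section 5 claims blinding for the interviewing physician only; diffusion in the room is likely to be apparent to the ward staff who manage the patient. If withdrawals relate to how patients are doing, the patients left in the comparison are no longer the two groups that were randomised.

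Relaxing the 8-day rule alone would not solve this, because it cannot restore a T3 score that was not taken.

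**Working it through.** **Inputs**

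- Section 7: 32 patients, 16 per group.
- Sections 8.1.1 to 8.1.4: T1 = day 0, T2 = day 3, T3 = day 6, T4 = day 12.
- Section 5: withdrawn patients are evaluated only after 8 days of treatment.
- SAP: outcome = T3 − T1.
- Assumptions made here: treatment starts at T1, and a visit due on the day of withdrawal is done.

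**Step 1: the plan's own figure.** Section 7 lists 8 blocks of 4: 8 × 4 = 32, with 16 A and 16 B. This agrees with the stated size. Each patient is 1/16 = 6.25% of an arm.

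**Step 2: day of withdrawal against visits and the 8-day rule.**

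| Withdrawn on day | Ratings held | Ratings with no plan | 8-day rule | T3 − T1 |
|---|---|---|---|---|
| 1–2 | T1 | T2, T3, T4 | not evaluated | not obtainable |
| 3–5 | T1, T2 | T3, T4 | not evaluated | not obtainable |
| 6–7 | T1, T2, T3 | T4 | not evaluated | exists, but set aside |
| 8–11 | T1, T2, T3 | T4 | evaluated | exists and used |

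Two separate losses affect the SAP comparison: T3 is not planned (days 1–5), and T3 is held but not used (days 6–7).

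**Step 3: does return to standard care end the ratings?** The text does not say so outright. Three passages point that way:

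- Section 8.1.1 sets being followed in the project against following the standard process, as alternatives.
- The section 5 list of tests to be done within 48 hours omits the NPI-NH, which the section then assigns, for this study, to one physician now working in another department.
- If evaluated in the 8-day sentence means assessed, early leavers are expressly not assessed. If it means analysed, their remaining visits still appear nowhere.

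On either reading, a patient withdrawn before day 6 has no planned T3.

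**Step 4: can direction and size be derived?** Let k be the number lost in an arm, m the mean improvement of those kept and l that of those lost. The all-allocated mean is m − (k/16)(m − l). The kept-patient difference (B minus A) therefore exceeds the all-allocated difference by

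(k_B/16)(m_B − l_B) − (k_A/16)(m_A − l_A).

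With assumed values m − l = 8 points:

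- 3 lost in B, none in A: 3 × 8/16 = +1.5 points;
- 3 lost in each arm: 1.5 − 1.5 = 0;
- 3 lost in A, none in B: −1.5 points.

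The documents give none of k, m or l, so even the sign is open.

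**The case against.** The strongest reply is that the quoted sentence concerns care, not assessment. The synopsis and sections 3 and 8 describe the tests as part of routine practice, and the lists in the synopsis and section 8 include the NPI-NH, so standard care does not by itself exclude a further rating. This stands in part. A reader might infer that the protocol forbids ratings after withdrawal, or that outcome data end whenever treatment ends. Neither is stated. What the documents support is that no rating is scheduled, with the strong inference in step 3 that none would be done.

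Other points also stand:

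- A reader might list stopping the oils for safety as a third route. The text has two, and it does not say that a consenting patient who stops the oils becomes withdrawn. Section 8 even foresees adapting the oils within the 14 days. Whether that covers a complete stop is unclear, which is the gap itself.
- A reader might cite a day-9 withdrawal as a lost outcome. That patient already has T3, so the SAP comparison is unaffected, and T4 may be allowed by the 8-day exception.
- A reader might conclude that the comparison favours Group B, by some 7% to 33%. Those figures come from placing 1 to 4 non-improving losses in Group B alone, with 8 points of improvement in the rest. Section 5 allows withdrawal in either arm, and both arms are exposed to psychotropic side effects (section 4).

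The study is also a 32-patient pilot that the protocol calls descriptive (section 13). That lowers the stakes but does not remove the point: a descriptive comparison of selected patients is still selected, and the SAP does test T3 − T1.

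**Conclusion.** The point holds as a gap in outcome collection joined to an exclusion rule. Section 5 merges stopping treatment with leaving the study. As written, it plans no T3 for anyone withdrawn before day 6 and sets aside the T3 of anyone withdrawn on day 6 or 7. The SAP comparison would then omit randomised patients for post-randomisation reasons that may differ by arm. The 8-day rule is justified by aromatherapy efficacy, and what counts as being treated in Group A is not defined.

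The conclusion rests on reading return to standard care as the end of scheduled study ratings, which the protocol implies but does not state. The size is 6.25% of an arm per patient omitted. The number omitted, and the direction and size of any bias, cannot be derived from the documents.

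**What to change.** In section 5, define two statuses:

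> (a) Study treatment stopped, consent to data collection intact: the patient stays in the study, and the remaining T2, T3 and T4 NPI-NH and staff-distress ratings are done by interview while the patient is on the ward. (b) Consent to data collection withdrawn: no further study ratings are done.

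Amend the standard-care sentence and the 8-day sentence together. If the 8-day sentence were left as it is, it would contradict the new text. State that all available scores, as far as consent allows, are analysed in the allocated group whatever the duration of treatment. Report the number, date and reason for each status by arm. Repeat the rule in the SAP.

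The cost is small. The physician is already appointed, and the patient need not be present: "The physician, by interview with patient's nurse, in absence of patient himself, will fill out the NPI-NH". There are a few extra interviews with nurses, care assistants and resident physicians. The sample size stays at 32. The observed effect may change or look smaller.

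The SAP is written in the past tense, so ratings not taken may be beyond recovery. Using the T3 scores already held for patients withdrawn on day 6 or 7, and reporting withdrawals by arm, may still be possible. The change concerns data collection and analysis only and sets no rule for when treatment should stop.
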